Approximately 550 participants will be enrolled at a **CCI**. A sample size of 100 participants in one group has at least an 85% (or 95%) probability to observe at least 1 participant with an AE at a true 2% (or 3%) AE rate (see table below).

Randomized Sample Size Calculations

Sample Size	True AE Rate	Probability to Observe 0 AEs	Power to Detect at Least 1 AE
50	0.05	7.7%	92.3%
50	0.03	21.8%	78.2%
100	0.03	4.8%	95.2%
100	0.02	13.3%	86.7%

Abbreviation: AE = adverse event.

Analysis Sets:

Set	Description
Randomization Set	The randomization set consists of all participants who are randomly assigned.

1	
FAS ¹	The FAS consists of all randomly assigned participants who receive the IP.
PP Set ²	The PP set consists of all participants in the FAS who comply with the injection schedule, comply with the timings of immunogenicity blood sampling to have a baseline and at least 1 post-injection assessment, do not have influenza or SARS-CoV-2 infection at baseline and post-baseline up to Day 29 (as documented by positive RT-PCR testing result), and have no major protocol deviations and/or prohibited concomitant medication use (documented in Section 6.5.3) that are prespecified with impacts on the immune response and should be excluded from the PP set.
Safety Set ³	The safety set consists of all randomly assigned participants who receive the IP.
Solicited Safety Set ⁴	The solicited safety set consists of all participants in the safety set who contribute any solicited AR data.

Abbreviations: AR = adverse reaction; FAS = full analysis set; IP = investigational product; PP = per-protocol.

Safety Analyses:

All safety analyses are descriptive in nature and will be based on the Safety Set, except summaries of solicited ARs, which will be based on the Solicited Safety Set. All safety analyses will be provided by study arm. Participants will be included in the vaccination group corresponding to what they actually received. Local solicited reactogenicity analysis will be presented by study group and for each injection content, respectively.

Safety and reactogenicity will be assessed by clinical review of all relevant parameters, including solicited ARs (local and systemic ARs); unsolicited AEs (including any clinical safety laboratory abnormalities); treatment-related AEs; severe AEs, SAEs, MAAEs, AESIs, and AEs leading to withdrawal from study participation; vital sign measurements; and physical examination findings.

The number and percentage of participants with any solicited local AR, with any solicited systemic AR, with any solicited AR during the 7-day follow-up period after each vaccination, and with any Grade 3 or higher solicited AR will be summarized. A 2-sided 95% exact confidence interval (CI) using the Clopper-Pearson method will be provided for the percentage of participants with any solicited AR.

¹ For the FAS, participants will be analyzed according to the group to which they were randomized.

² The PP set will be used as the primary analysis set for analyses of immunogenicity unless otherwise specified. Participants will be analyzed according to the group to which they were randomized.

³ The safety set will be used for all analyses of safety, except for the solicited ARs. Participants will be included in the vaccination group corresponding to what they actually received.

⁴ The solicited safety set will be used for the analyses of solicited ARs and participants will be included in the vaccination group corresponding to what they actually received.

The number and percentage of participants with unsolicited AEs, treatment-related AEs, severe AEs, SAEs, MAAEs, AESIs, and AEs leading to withdrawal will be summarized. Unsolicited AEs will be presented by Medical Dictionary for Regulatory Activities (MedDRA) system organ class and preferred term. Unsolicited AEs will be coded according to the MedDRA Dictionary for Adverse Reaction Terminology.

The number of events of solicited ARs, unsolicited AEs/SAEs, MAAEs, AEs leading to withdrawal, and AESIs will be reported in summary tables accordingly. Pregnancy outcomes will also be summarized.

For all other safety parameters, descriptive summary statistics will be provided. Further details will be described in the statistical analysis plan (SAP).

Immunogenicity Analyses:

The analyses of immunogenicity will be based on the per-protocol (PP) set. If the number of participants in the full analysis set (FAS) and PP set differs (defined as the difference divided by the total number of participants in the PP set) by more than 10%, supportive analyses of immunogenicity may be conducted using the FAS.

For the immunogenicity endpoints, the geometric mean of specific antibody titers with corresponding 95% CI at each time point and the geometric mean fold rise (GMFR) of specific antibody titers with the corresponding 95% CI at each post-baseline time point over preinjection baseline at Day 1 will be provided by treatment arm, with adjustment for baseline antibody titer and other potential covariates, including age group and primary vaccine type. Descriptive summary statistics, including median, minimum, and maximum, will also be provided.

For summarizations of geometric mean titer, antibody titers reported as below the lower limit of quantification (LLOQ) will be replaced by $0.5 \times LLOQ$. Values that are greater than the upper limit of quantification (ULOQ) will be converted to the ULOQ.

For mRNA-1010, seroconversion rate from baseline will be provided with a 2-sided 95% CI using the Clopper-Pearson method at each post-baseline time point. Rate of seroconversion is defined as the proportion of participants with either a pre-vaccination HAI titer < 1:10 and a post-vaccination HAI titer $\ge 1:40$ or a pre-vaccination HAI titer $\ge 1:10$ and a minimum 4-fold rise in post-vaccination HAI antibody titer.

For mRNA-1273, seroresponse is defined as either: participants with GMFR in nAb or (binding antibody) bAb titers of \geq 4-fold at Day 29 compared to Day 1 in those with baseline titer \geq LLOQ, or Day 29 titer \geq 4 × LLOQ if baseline titer is \leq LLOQ.

The immunogenicity of mRNA-1073 will follow the same rules as mRNA-1010 and mRNA-1273.

Planned Analyses:

An interim analysis (IA) and a final analysis will be conducted in the study.

The IA will be performed after all the 550 participants randomized into Group 1 through Group 6 have completed their Day 29 visit assessments and will include the safety and immunogenicity data collected up to Day 29. Either nAb or bAb assay will be used for assessment of immunogenicity. The IA will be performed by a separate team of unblinded programmers and statisticians. The analysis will be presented by vaccination groups. Except for a limited number of Sponsor and CRO personnel who will be unblinded to perform the IA, the study site staff, investigators, study monitors, and participants will remain blinded until after the final database lock for final analysis.

The final analysis of all endpoints will be performed after all participants have completed Day 181/EoS. Results of this analysis will be presented in a final clinical study report (CSR), including individual listings. The final CSR will include full analyses of all safety and immunogenicity data through Day 181/EoS. For immunogenicity analysis, either nAb or bAb assays will be used in the study.

(clinic) (clinic) (clinic)

[figure not shown]
(clinic)

(clinic)

(safety call)

1.2. Schema

Figure 1 Study Schema

[figure not shown]

(safety call)

Unscheduled visits (Day 1 to Day 181)

(safety call)

(safety call)

Assessments per SoE in Table 1

Abbreviations: SoE = schedule of events; V = visit.

1.3. Schedule of Events

 Table 1
 Schedule of Events

Visit Number	SCRN	1	2	3	4	5, 6, 7, 8	9	USV
Type of Visit	С	С	С	С	С	SC	С	С
Month Time Point	N/A				M1	M2-M5	M6	Up to M6
Visit Day	Screening ¹	D1 (Baseline) ¹	D4	D8	D29	D57, D91, D121, D151	D181/ EoS	N/A
Window Allowance (Days)	-28	N/A	-2	+3	-7 to +2	±5	±14	N/A
Informed consent form, demographics, concomitant medications, medical history	X							
Inclusion/exclusion criteria	X	X						
Blood collection for safety laboratory samples ²	X			X				
Full physical examination ³	X							
Axillary lymph nodes assessment (both arms) ⁴		X						
Symptom-directed physical examination ⁵		X		X	X		X	X
Vital sign measurements ⁶	X	X						
Electrocardiogram (ECG) ⁷		X						
Pregnancy testing ⁸	X	X						
Randomization		X						
Study vaccination (including 60-minute, post-dose observation period)		X ⁹						
Blood collection for humoral immunogenicity ¹⁰		X		X	X		X	
Blood collection for cellular immunogenicity ¹⁰		X		X	X		X	
Optional blood collection for genomics ¹¹		X						
Optional blood collection for transcriptomics ¹¹		X		X	X			
Blood sample for potential biomarker analysis ¹²			X					
Nasopharyngeal swab for virus detection ¹³		X						X
eDiary activation for recording solicited ARs (7 days) ¹⁴		X						

Visit Number	SCRN	1	2	3	4	5, 6, 7, 8	9	USV
Type of Visit	С	С	С	С	С	SC	С	С
Month Time Point	N/A				M1	M2-M5	M6	Up to M6
Visit Day	Screening ¹	D1 (Baseline) ¹	D4	D8	D29	D57, D91, D121, D151	D181/ EoS	N/A
Window Allowance (Days)	-28	N/A	-2	+3	-7 to +2	±5	±14	N/A
Review of solicited AR eDiary				X				
eDiary activation for Symptom Reporting eDiary ¹⁵		X						
Symptom Reporting eDiary for collection of symptoms of ILI and/or COVID-19 ¹⁶		Once weekly						
Follow-up safety call ¹⁷						X		
Recording of unsolicited AEs through Day 29		X		X	X			X
Recording of SAEs, AESIs, MAAEs, AEs leading to discontinuation, and concomitant medications relevant to or for their treatment ¹⁸		X		X	X	X	X	X
Recording of non-study vaccinations ¹⁸	X	X		X	X	X	X	X
Study completion							X	

Abbreviations: AE = adverse event; AESI = adverse event of special interest; ALT = alanine aminotransferase; AR = adverse reaction; AST = aspartate aminotransferase; C = clinic visit; COVID-19 = coronavirus disease 2019; D = day; ECG = electrocardiogram; eDiary = electronic diary; EoS = end of study; ILI = influenza-like illness; IM = intramuscular; M = month; MAAE = medically attended adverse event; N/A = not applicable; NP = nasopharyngeal; SAE = serious adverse event; SARS-CoV-2 = severe acute respiratory syndrome coronavirus 2; SC = safety (phone) call; SCRN = Screening; USV = unscheduled visit.

- ^{1.} Screening and Day 1 will NOT be performed on the same day. Additionally, the Screening Visit may be performed over multiple visits if within the 28-day Screening window.
- ² Safety laboratory tests: Total white blood cell count, hemoglobin, platelets, ALT, AST, creatinine, alkaline phosphatase, and total bilirubin.
- ^{3.} Physical examination: A full physical examination, including height and weight, will be performed at Screening. Interim physical examinations will be performed at the discretion of the investigator. Any clinically significant finding identified by a healthcare professional during study visits should be reported as an MAAE.
- ⁴ On the day of vaccination, prior to injection, axillary lymph nodes of both arms should be examined, and any abnormalities should be documented.
- ⁵ Symptom-directed physical examinations will be performed at all clinic visits, except at Screening, where a full physical examination will be performed. Interim physical examinations will be performed at the discretion of the investigator. Any clinically significant finding identified by a healthcare professional during study visits should be reported as an MAAE.

mRNA 1073-P101 Protocol Amendment 2 mRNA-1073

- ⁶ Vital sign measurements: Systolic and diastolic blood pressure, heart rate, respiratory rate, and body temperature. The preferred route of temperature assessment is oral. Vital signs will only be collected at Screening and on the day of vaccination (Day 1), once before and at least 60 minutes after vaccination. Vital signs will be collected at other clinical visits only in conjunction with a symptom-directed physical examination.
- ⁷ A 12-lead ECG will be obtained, after 10 minutes of supine rest, at Visit 1/Day 1 prior to vaccination.
- ⁸ A point-of-care urine pregnancy test will be performed at the Screening Visit and before the IM injections on Day 1. At the discretion of the investigator, a pregnancy test either via blood or point-of-care urine can be performed at any time. The follicle-stimulating hormone level may be measured at the Screening Visit, as necessary, and at the discretion of the investigator, to confirm menopausal status.
- ⁹. All participants will be randomized to receive 2 IM injections, one in each arm, in the deltoid muscle.
- Samples for humoral immunogenicity and cellular immunogenicity must be collected prior to receipt of vaccination on Day 1. Cellular immunogenicity will be sampled and assessed in a subset of participants.
- Transcriptomic and genomic samples will be part of the optional biomarker assessment once consented by the study participant. Blood draws on Day 1 must occur prior to participants being vaccinated.
- Biomarker plasma and biomarker serum samples will be stored for potential future biomarker assessment.
- An NP swab specimen for pathogens, including influenza and SARS-CoV-2, will be collected prior to the study injections on Day 1 to document any pre-vaccination infection. An NP swab will also be collected through study completion if any signs or symptoms or an MAAE suggesting influenza, COVID-19, or other causes of upper or lower respiratory infection occur. For signs or symptoms during the study, a participant will be instructed to contact the study site to have an NP swab collected for testing. If the participant cannot or is unable to come into the site to perform the NP swab, every effort should still be made by the site to obtain the NP swab (eg, home visits to collect NP swab for central laboratory testing). Local laboratory testing for influenza and SARS-CoV-2 can be performed in these cases as a backup if NP swab cannot be collected for central laboratory testing.
- The eDiary entries will be recorded by the participant starting approximately 60 minutes after vaccination while at the clinic with instruction provided by study staff. Study participants will continue to record in the eDiary each day after they leave the clinic, preferably in the evening and at the same time each day, on the day of vaccination and for 6 days following vaccination. Local solicited ARs will be recorded separately for each injection site. Please see Section 8.4.3 for details.
- The Symptom Reporting eDiary will be activated for collection of ILI and COVID-19 symptoms.
- Symptom Reporting eDiary: Participants will be instructed to report via eDiary or telephone calls whether ILI and/or COVID-19 symptoms have been experienced on the following schedule: Once weekly from Day 1 through Day 181/EoS, if symptoms occur, participants will be directed to return to the study site as soon as possible, but no later than 72 hours after the onset of symptoms, for medical evaluation and an NP swab.
- Trained study personnel will call all participants to collect information related to any SAEs, MAAEs, AESIs, AEs leading to discontinuation, information on concomitant medications associated with those events, and any non-study vaccinations.
- All concomitant medications and non-study vaccinations will be recorded through 28 days after vaccination; all concomitant medications relevant to or for the treatment of an SAE, AESI, or MAAE will be recorded from Screening through Day 181/EoS. Historical use of facial injections and dermal fillers for cosmetic or medical indications such as migraine headaches will also be collected.

TABLE OF CONTENTS

CLINIC	AL STUDY PROTOCOL	1
PROTO	COL APPROVAL – SPONSOR SIGNATORY	2
DECLA	RATION OF INVESTIGATOR	3
PROTO	COL AMENDMENT SUMMARY OF CHANGES	4
1.	PROTOCOL SUMMARY	9
1.1.	Synopsis	9
1.2.	Schema	25
1.3.	Schedule of Events	26
TABLE	OF CONTENTS.	29
LIST O	F TABLES	36
LIST O	F FIGURES	36
LIST O	F ABBREVIATIONS AND DEFINITION OF TERMS	37
2.	INTRODUCTION	40
2.1.	Background and Overview	40
2.1.1.	mRNA-1010	41
2.1.2.	mRNA-1273	41
2.1.3.	mRNA-1073	42
2.2.	Study Rationale	42
2.2.1.	Nonclinical Studies	42
2.2.2.	Clinical Studies	44
2.3.	Benefit/Risk Assessment	45

	aTX, Inc. 1073-P101 Protocol Amendment 2	mRNA-1073
2.3.1.	Potential Benefits of Study Participation	45
2.3.2.	Risks from Study Participation and Their Mitigation	45
2.3.3.	Overall Benefit/Risk Conclusion	46
3.	OBJECTIVES AND ENDPOINTS	48
4.	STUDY DESIGN	50
4.1.	General Design	50
4.2.	Scientific Rationale for Study Design	52
4.3.	Choice of Vaccine Doses	53
4.4.	End of Study Definition	54
5.	STUDY POPULATION	55
5.1.	Inclusion Criteria	55
5.2.	Exclusion Criteria	56
5.3.	Lifestyle Restrictions	57
5.4.	Screen Failures	58
6.	STUDY TREATMENT	59
6.1.	Investigational Products Administered	59
6.2.	Randomization and Blinding	59
6.3.	Preparation/Handling/Storage/Accountability	60
6.3.1.	Preparation of Study Vaccine	60
6.3.2.	Study Vaccine Administration	60

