3. OBJECTIVES AND ENDPOINTS

The objectives and endpoints of this study are described in Table 2.

Table 2 Study Objectives and Endpoints

Objectives	Endpoints
·	"F"
To evaluate the safety and reactogenicity of study vaccines	 Frequency and grade of each solicited local and systemic reactogenicity AR during a 7-day follow-up period post vaccination Frequency and severity of any unsolicited AEs during the 28-day follow-up period post vaccination Frequency of any SAEs, AESIs, MAAEs, and AEs leading to discontinuation from Day 1 to Day 181/EoS
Secondary	
To evaluate the humoral immunogenicity to vaccine-matched strains for influenza and SARS-CoV-2 across study vaccine arms at Day 29	 GMT and GMFR at Day 29 compared with Day 1 (baseline) by HAI assay for influenza and PsVNA (or binding antibody assay) for SARS-CoV-2 Influenza: Percentage of participants with seroconversion, defined as a Day 29 titer ≥ 1:40 if baseline is < 1:10 or a 4-fold or greater rise if baseline is ≥ 1:10 in anti-HA antibodies measured by HAI assay SARS-CoV-2: Percentage of participants with seroresponse, defined as a Day 29 titer ≥ 4-fold if baseline is ≥ LLOQ or ≥ 4 × LLOQ if baseline titer is < LLOQ in nAb titers measured by PsVNA (or binding antibody assay)
To evaluate the humoral immunogenicity to vaccine-matched strains for influenza and SARS-CoV-2 at all evaluable humoral immunogenicity time points	 GMT and GMFR compared with Day 1 (baseline) by HAI for influenza and PsVNA (or binding antibody assay) for SARS-CoV-2 Percentages of participants with seroconversion (influenza) and seroresponse (SARS-CoV-2) as defined above

Objectives	Endpoints
Exploratory (may be performed)	
To evaluate the humoral immunogenicity against vaccine mismatched strains	GMT and GMFR (compared to Day 1) to vaccine mismatched strains
To evaluate the humoral immunogenicity against vaccine-matched and mismatched strains using alternative methods	GMT and GMFR (compared to Day 1) to vaccine-matched and mismatched strains assayed by alternative methods (eg, microneutralization assay for influenza or ligand-binding assay for SARS-CoV-2)
To evaluate cellular immunogenicity in a subset of participants	Frequency, magnitude, and phenotype of virus-specific T-cell and B-cell responses measured by flow cytometry or other methods, and to perform targeted repertoire analysis of B cells and T cells after vaccination

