Participants will have 6 visits and 4 safety phone calls. Vaccines (mRNA-1073, mRNA-1010, or mRNA-1273) and placebo (as indicated) will be administered as IM injections, one in each arm, in the deltoid muscle. Safety and/or immunogenicity and/or biomarkers study visits will occur on Days 4, 8, 29, and 181 (end of study [EoS]). Study visits will include scheduled safety phone calls at Days 57, 91, 121, and 151 to collect adverse events (AEs), medically attended AEs (MAAEs), AEs of special interest (AESIs), AEs leading to withdrawal, serious adverse events (SAEs), and information about concomitant medications and receipt of non-study vaccinations.

At the dosing visit on Day 1, participants will be instructed how to record solicited ARs within the provided electronic diary (eDiary). Solicited ARs will be collected for 7 days (the day of injection and the following 6 days), and local solicited ARs will be collected separately for each injection site. Unsolicited AEs will be collected for 28 days (the day of injection and the following 27 days) after injection; SAEs, MAAEs, AEs leading to withdrawal, and AESIs will be collected throughout the study. All participants will be tested for the presence of SARS-CoV-2 and influenza antigens at baseline via nasopharyngeal (NP) swabs (Day 1) and at any unscheduled visits. Blood draws will be collected on Days 1, 8, 29, and 181/EoS. There will be an additional visit on Day 4 at which blood will be drawn for future biomarker assessment. Optionally, blood draws for genomic analysis will be collected at Day 1 and for transcriptomic analysis at Days 1, 8, and 29. The collected samples will be processed and analyzed per the Laboratory Manual. Active surveillance for intercurrent or breakthrough SARS-CoV-2 infection will occur throughout the study and reported as AEs (confirmed symptomatic infections will be reported as MAAEs if not SAEs). Participants with signs and symptoms meeting the CDC case definition for COVID-19 (21 February 2021 or most recent; CDC 2021b) will be asked to contact the site and undergo prompt assessment, which will include reverse transcriptase polymerase chain reaction (RT-PCR) testing (of a respiratory sample) to assess symptomatic COVID-19. Participants with any clinical or radiographic evidence of pneumonia will also

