8.1. Safety Assessments and Procedures

Safety assessments will include monitoring and recording of the following for each participant, according to the SoE (Table 1):

• Solicited local and systemic ARs (Section 8.4.3) that occur during the 7 days following vaccine administration (ie, the day of study injections [Day 1] and 6 subsequent days).

Solicited ARs will be recorded daily using electronic diaries (Section 8.1.1). Local solicited ARs will be recorded separately for each injection site.

- Unsolicited AEs observed or reported during the 28 days following vaccination (ie, the day of injection [Day 1] and 27 subsequent days). Unsolicited AEs are defined in Section 8.4.1.
- SAEs, AESIs, MAAEs, and AEs leading to discontinuation from study participation from vaccination on Day 1 through Day 181/EoS or withdrawal from the study.
- Results of safety laboratory tests (Section 8.1.5).
- Vital sign measurements (Section 8.1.4).
- Physical examination findings (Section 8.1.6).
- Symptom Reporting eDiary for ILI and COVID-19 from Day 1 through Day 181/EoS as described below in Section 8.1.8.
- Details of all pregnancies in female participants will be collected after the start of study treatment and until the end of their participation in the study (Section 8.4.8).

The incidence and severity of the above events will be monitored by an IST as per the charter.

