Myalgia (muscle aches all over body)	No interference with activity	Some interference with activity	Significant; prevents daily activity	Requires emergency room visit or hospitalization
Arthralgia (joint aches in several joints)	No interference with activity	Some interference with activity	Significant; prevents daily activity	Requires emergency room visit or hospitalization

Reaction	Grade 1	Grade 2	Grade 3	Grade 4
Nausea/vomiting	No interference with activity or 1-2 episodes/ 24 hours	Some interference with activity or > 2 episodes/24 hours	Prevents daily activity, requires outpatient intravenous hydration	Requires emergency room visit or hospitalization for hypotensive shock
Chills	No interference with activity	Some interference with activity not requiring medical intervention	Prevents daily activity and requires medical intervention	Requires emergency room visit or hospitalization
Fever (oral)	38.0-38.4°C 100.4-101.1°F	38.5-38.9°C 101.2-102.0°F	39.0-40.0°C 102.1-104.0°F	> 40.0°C > 104.0°F

Abbreviations: AE = adverse event; eCRF = electronic case report form.

Note: Events listed above but starting > 7 days post study injection will be recorded on the AE page of the eCRF. Causality for each event will be determined per assessment by the Investigator.

Source: Modified from DHHS 2007.

Any solicited AR that meets any of the following criteria must be entered into the participant's source document and must also be recorded by the study site staff on the reactogenicity page of the participant's eCRF:

- Solicited local or systemic AR that results in a visit to a healthcare practitioner (HCP), to be recorded as an MAAE (Section 8.4.4).
- Solicited local or systemic AR leading to the participant withdrawing from the study or the participant being withdrawn from the study by the investigator (AE leading to withdrawal).
- Solicited local or systemic AR lasting beyond 7 days post injection.
- Solicited local or systemic AR that otherwise meets the definition of an SAE.

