8.4.9. Eliciting and Documenting Adverse Events

The investigator is responsible for ensuring that all AEs and SAEs are recorded in the eCRF and reported to the Sponsor.

Solicited ARs will be collected from Day 1 through 7 days after vaccination. Other (unsolicited) AEs will be collected from Day 1 through 28 days after vaccination.

The MAAEs, AESIs, AE leading to withdrawal, and SAEs will be collected from participants as specified in the SoE (Table 1) until the end of their participation in the study. Any AEs occurring before receipt of IP will be analyzed separately from AEs occurring after receipt of the study vaccine(s).

At every study site visit or telephone contact, participants will be asked a standard question to elicit any medically related changes in their well-being (including respiratory viral infection and COVID-19 symptoms) according to the scripts provided. Participants will also be asked if they have been hospitalized, had any accidents, used any new medications, changed concomitant medication regimens (both prescription and over-the-counter medications), or had any non-study vaccinations.

In addition to participant observations, physical examination findings, or data relevant to participant safety classified as an AE will be documented on the AE page of the eCRF.

After the initial AE/SAE report, the investigator is required to proactively follow each participant at subsequent visits/contacts. All AEs and SAEs will be treated as medically appropriate and followed until resolution, stabilization, the event is otherwise explained, or the participant is LTFU (as defined in Section 7.4). All contacts, or contact attempts, concerning follow-up of AEs/SAEs should be recorded in the participant's source documentation.

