8.4.14. Reporting of Adverse Events of Special Interest

The following process for reporting an AESI ensures compliance with 21 CFR 312 and ICH GCP guidelines. After learning that a participant has experienced an AESI, the investigator or

designee is responsible for reporting the AESI to the Sponsor, regardless of relationship or expectedness, within 24 hours of becoming aware of the event. If the AESI meets the criteria for an SAE, the SAE reporting procedure should be followed.

8.4.15. Time Period and Frequency for Collecting Adverse Event and Serious Adverse Event Information

Medical occurrences that begin before IP dosing but after obtaining informed consent will be recorded in the Medical History/Current Medical Conditions section of the eCRF and not in the AE section; however, if the condition worsens at any time after IP administration, it will be recorded and reported as an AE.

Adverse events may be collected as follows:

- Observing the participant.
- Receiving an unsolicited complaint from the participant.
- Questioning the participant in an unbiased and nonleading manner.

Solicited ARs will be collected from the day of injection through 6 days after vaccination. Other (unsolicited) AEs will be collected from the day of injection through 28 days after vaccination.

Serious AEs (including AESIs) will be collected from the start of IP dosing until the last day of study participation.

All SAEs and AESIs will be recorded and reported to the Sponsor or designee immediately, and under no circumstance should this exceed 24 hours of becoming aware of the event via the EDC system. If a site receives a report of a new SAE or AESI from a study participant or receives updated data on a previously reported SAE or AESI and the eCRF has been taken offline, then the site can report this information on the paper SAE/AESI report form provided by the Sponsor.

An abnormal value or result from a clinical or laboratory evaluation can also indicate an AE if it is determined by the investigator to be clinically significant (eg, leads to study drug discontinuation or meets any serious criteria). If this is the case, it must be recorded in the source document and as an AE on the appropriate AE form(s). The evaluation that produced the value or result should be repeated until that value or result returns to normal or is stabilized and the participant's safety is not at risk.

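### The last scheduled contact marked for unsolicited AEs can fall on Day 22, before the primary 28-day period ends, and the protocol contradicts itself on whether later calls collect them

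*Protocol*

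**What the plan says.** A primary endpoint (Protocol Section 3) is "Frequency and severity of any unsolicited AEs during the 28-day follow-up period post vaccination".

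**Collection points.** In Table 1 the row "Recording of unsolicited AEs through Day 29" is marked at the Day 1, Day 8 and Day 29 visits and at unscheduled visits. It is not marked at the Day 57, 91, 121 and 151 safety calls. The Day 29 visit has a window of -7 to +2 days, and the calls have ±5 days.

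**Content of the calls.** The Table 1 footnote says "Trained study personnel will call all participants to collect information related to any SAEs, MAAEs, AESIs, AEs leading to discontinuation", plus related medications and non-study vaccinations. Ordinary unsolicited AEs are not listed. Sections 4.1 and 8.1.2, however, put AEs among the items the calls gather, and Section 8.4.9 requires a standard well-being question at every visit or telephone contact.

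**End of the period.** Section 4.1 says "Unsolicited AEs will be collected for 28 days (the day of injection and the following 27 days) after injection". Section 8.1 agrees: "Unsolicited AEs observed or reported during the 28 days following vaccination (ie, the day of injection [Day 1] and 27 subsequent days"; so does the Synopsis. Section 8.4.15 says "Other (unsolicited) AEs will be collected from the day of injection through 28 days after vaccination", Section 8.4.9 is worded to the same effect, and the Table 1 row runs to Day 29.

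**Solicited reactions.** Sections 8.1, 8.4.3 and 8.4.15 count the injection day plus 6 days. Section 8.4.9 says "Solicited ARs will be collected from Day 1 through 7 days after vaccination". The note to Table 6 says "Events listed above but starting > 7 days post study injection will be recorded on the AE page of the eCRF".

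**The concern.** A 28-day AE endpoint needs a contact at or after the end of the 28 days at which those AEs are asked about. Here the last scheduled contact marked for the purpose can come almost a week too soon, and the protocol gives two answers on whether the next contact covers the gap. A site following Table 1 and its footnote would not ask about ordinary AEs on Day 57; a site following Section 8.1.2 would.

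The likely effect is that AEs starting late in the period are missed or reported late, which lowers the observed frequencies. The interim analysis takes place once all 550 participants have completed their Day 29 visits, so it would include everyone seen early. The SAP can choose Day 28 or Day 29 as the cut-off, but it cannot recover events that no contact was clearly required to collect.

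**Working it through.** **1. Range of the Day 29 visit.** 29 - 7 = Day 22; 29 + 2 = Day 31. Of these ten permitted days, six (Days 22 to 27) come before Day 28 and seven (Days 22 to 28) come before Day 29.

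**2. Days after the last marked contact, for a Day 22 visit.** Share = (end day - visit day) / length of period.
- End on Day 28: (28 - 22)/28 = 6/28 = 21.4%.
- End on Day 29: (29 - 22)/29 = 7/29 = 24.1%.

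These count the visit day as observed. If it is not counted, the shares are 7/28 = 25.0% and 8/29 = 27.6%.

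**3. Average over visits (assumption: visits spread evenly over Days 22 to 31; the protocol gives no distribution).**
- To Day 28: (6+5+4+3+2+1+0+0+0+0)/10 = 2.1 days; 2.1/28 = 7.5%.
- To Day 29: (7+6+5+4+3+2+1+0+0+0)/10 = 2.8 days; 2.8/29 = 9.7%.

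**4. Recall interval if the Day 57 call does collect AEs.** The call falls on Days 52 to 62. For onset on Days 23 to 28, the shortest interval is 52 - 28 = 24 days and the longest is 62 - 23 = 39 days.

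**5. The plan's own safety figure.** Table 7 uses 1 - (1 - p)^n. All four rows reproduce: n=50, 5%: 92.3%; n=50, 3%: 78.2%; n=100, 3%: 95.2%; n=100, 2%: 86.7%.

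As an outer bound only, suppose that every participant is last seen on Day 22, onset is uniform over the period, and nothing is captured later. For n=100 and a true rate of 2%:
- 28-day period: 1 - (1 - 0.02 × 22/28)^100 = 79.5%.
- 29-day period: 1 - (1 - 0.02 × 22/29)^100 = 78.3%.

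If onsets cluster early and only 5% or 10% fall in the unobserved days, the probability is 85.3% or 83.7%. None of these onset patterns is given in the protocol.

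**6. Is there another rule that closes the gap?** Section 6.4 carries safety requirements forward to the next visit, but only for a missed visit. A Day 22 visit is within its window and triggers nothing.

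**The case against.** The best reply is that nothing in the protocol says collection stops at the Day 29 visit. The row itself runs through Day 29, unscheduled visits are marked in it, and several sections provide for later capture: Sections 4.1 and 8.1.2 on the calls, Section 8.4.9 on every telephone contact, Section 8.4.12 on reporting all AEs observed or reported during the study, and Section 8.4.16 on diary space for unsolicited AEs. SAEs, AESIs, MAAEs and AEs leading to discontinuation are recorded to Day 181, and an MAAE includes an unscheduled contact with a healthcare practitioner even by telephone. All six groups share one visit window, assessments are blinded, and the analyses are descriptive.

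Much of this stands, and it rules out several stronger readings that a reader might infer:
- That the endpoint is truncated by a fixed share. Later capture is possible, and a share of days is not a share of events.
- That the endpoint has no single denominator. The two end days differ by one day, and Section 9.5.2 summarises percentages of participants, not person-time rates.
- That dose comparisons are biased. Nothing shows that visit timing differs by arm.
- That late reports always miss the interim. This applies only to participants whose Day 57 call follows the cut.
- That a solicited-type event starting on Day 8 has nowhere to go. Sections 8.4.1 and 8.4.3 already send it to the AE page; only the wording of Section 8.4.9 and the Table 6 note is out of line.
- That an early non-study vaccine is an automatic per-protocol exclusion. Section 6.5.3 makes it something that may affect evaluability, and exclusion criterion 10 already bars planned vaccination within 28 days after injection.

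The objection does not remove the contradiction over the calls, and the later capture it relies on is mostly recall some weeks after onset.

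**Conclusion.** The concern holds as a risk of under-ascertainment together with an internal contradiction. For the earliest attenders, 21% to 24% of the days of the primary unsolicited-AE period follow the last scheduled contact that Table 1 marks for it. The protocol disagrees with itself on whether the Day 57 call covers those days and on whether the period ends on Day 28 or Day 29.

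The exposure is mainly of AEs without medical attention that start after an early visit, and the effect would be on absolute frequencies. The number of events lost cannot be derived, because the documents give neither the spread of visit days nor the timing of onsets. The even-spread averages (7.5% and 9.7%) and the detection probabilities are illustrations that rest on the assumptions stated with them.

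**What to change.** - State one end day for unsolicited AEs in the Synopsis, Table 1 and Sections 4.1, 8.1, 8.4.9 and 8.4.15.
- Reconcile Table 1 and the safety-call footnote with Sections 4.1, 8.1.2 and 8.4.9, so that the Day 57 call explicitly collects unsolicited AEs with onset up to that day.
- Either set the early bound of the Day 29 visit so that it cannot precede the end of collection, or require a brief AE close-out contact (call or eDiary prompt) for anyone seen earlier.
- At the interim, report how many participants had an incompletely observed AE period.
- Align the solicited-window wording in Section 8.4.9 and the Table 6 note with Sections 8.1 and 8.4.3.
- Reconcile Section 5.3, which ties vaccine deferral to completion of the Day 29 visit (possibly Day 22), with the 28-day period in Section 6.5.3.

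The cost is a wording amendment plus either slightly less scheduling flexibility or one short extra contact for some participants.
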